5.2.1 Additional Study Restrictions

As noted in the inclusion criteria, patients or their partners of childbearing potential must practice true abstinence or use highly effective methods of contraception. True abstinence is defined as refraining from heterosexual intercourse for the duration of the study. Non-childbearing potential and highly effective methods of contraception are defined in [Section 5.2.1.1](#) and [Section 5.2.1.2](#), respectively.

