Within 1 week prior to performing any lumbar puncture, a blood sample will be tested locally for platelet count and prothrombin time to confirm that it is safe to proceed with the lumbar puncture. Other predose assessments may also be performed up to 1 week prior to dosing as specifically listed in [Table 3](#) including UHDRS, PBA-s, and weight.

The Period 2 MAD cohorts will be conducted in a sequential manner. Subsequent multiple-dose cohorts will not initiate until the criteria for dose escalation are met ([Section 4.4.1.3](#)).

Immediately after study drug administration in any cohort, all patients should be ambulatory and active for approximately 30 minutes postdose on all dosing days. The Investigator should note any weakness or fatigue during this period. Formal physical examinations targeting the neurological system will be performed postdose at the time points specified in [Table 3](#).

Patients will attend clinic visits Q4W for assessments of safety, PK, and PD. Patients in P2C1 will receive doses on Week 0, Week 8, and Week 16. Pending DEC/SMC recommendation, subsequent cohorts may receive doses Q8W or less frequently (e.g., on Week 0 and Week 12).

4.1.4.4 *Period 2 Follow-up*

All patients are required to complete follow-up assessments, including evaluations of safety, PD, PK, clinical effects, and MRI. Patients will be followed up for a minimum of 12 weeks after the last dose. Any postdose SAEs will be monitored until resolution.

4.1.5 *Early Termination Visit*

If a patient withdraws from the study early, the patient should complete an early termination visit. Refer to [Section 5.3](#) for information on early withdrawal from study drug or from the study.

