5.1 Inclusion Criteria

1. Documented ability to understand the written study ICF(s) and consent and has provided signed written informed consent prior to any study procedures
2. Ambulatory male or female
3. Age ≥ 25 to ≤ 60 years old
4. Body mass index $\leq 32 \text{ kg/m}^2$
5. Documented CAG triplet repeats ≥ 36 in the *HTT* gene
6. Documented heterozygosity at SNP3

7. Documented presence of the A variant of SNP3 on the same allele as the pathogenic CAG triplet expansion
8. Clinical diagnostic motor features of HD, defined as UHDRS Diagnostic Confidence Score = 4
9. UHDRS TFC scores ≥ 9 and ≤ 13
10. In the opinion of the Investigator, the patient is able to tolerate all study procedures, and is willing to comply with all other protocol requirements.
11. Willingness to practice highly effective contraception for the duration of the study and for [REDACTED] after the last dose of study drug, if patients or their partners are of childbearing potential. Non-childbearing potential and highly effective methods of contraception are defined in (Section 5.2.1.1 and Section 5.2.1.2). In addition, willingness to forego sperm or ova (egg) donation for the duration of the study and [REDACTED] months after completion of the study.

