5.2.1.2 Highly Effective Methods of Contraception

Contraception methods that can achieve a failure rate of <1% per year when used consistently and correctly are considered highly effective birth control methods. Such methods are defined as one of the following:

- True abstinence, defined as refraining from heterosexual intercourse for the duration of the study, when in line with the preferred and usual lifestyle of the patient
- Vasectomized partner (if that vasectomized partner is the sole sexual partner and has received medical assessment of the surgical success of the vasectomy)
- An intrauterine hormone-releasing system (IUS).
- Combined (estrogen and progesterone containing) hormonal contraception associated with inhibition of ovulation (oral, intravaginal or transdermal combined)
- Progesterone-only hormonal contraception associated with inhibition of ovulation (oral, injectable, or implantable)
- An intrauterine device (IUD)

In addition, male participants must be required to use a condom, as contraception requirement, for the duration of the study and, at minimum, until 5 months (i.e., 5 elimination half-lives) after the last WVE-003 dose.

Note that periodic abstinence (calendar, symptothermal, post-ovulation methods), withdrawal (coitus interruptus), spermicides only, and lactational amenorrhoea are not acceptable methods of contraception.

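### True abstinence is defined as ending with the study, while inclusion criterion 11 and the male condom rule also set an end point counted from the last dose

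*Combined protocol and SAP*

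**What the plan says.** Four parts of the protocol bear on how long protection against pregnancy lasts.

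- **Section 5.2.1** offers patients or partners of childbearing potential two routes: true abstinence, or a highly effective method. It then states: "True abstinence is defined as refraining from heterosexual intercourse for the duration of the study".
- **Section 5.2.1.2** lists abstinence among the highly effective methods, with the same limit: "True abstinence, defined as refraining from heterosexual intercourse for the duration of the study". It then adds a separate duty for male participants, who must use a condom "for the duration of the study and, at minimum, until 5 months (i.e., 5 elimination half-lives) after the last WVE-003 dose".
- **Section 5.1, criterion 11** (also in the synopsis) requires "Willingness to practice highly effective contraception for the duration of the study and for" a further period after the last dose. The length is blacked out, but it is legible that such a period exists.
- **Section 4.1.4** sets the Period 2 timetable: "Patients in P2C1 will receive doses on Week 0, Week 8, and Week 16", and "Patients will be followed up for a minimum of 12 weeks after the last dose". Period 1 follow-up runs from 12 to 24 weeks after the single dose (Section 4.1.3.2).

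Section 15.4 defines the end of the study as the last visit of the last patient. Table 3 labels each patient's own Week 28 visit as EOS.

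**The concern.** Criterion 11 sets an obligation with two limbs: the study, and a period counted from the last dose. Both definitions of true abstinence contain only the first limb. Abstinence is also the only entry in the Section 5.2.1.2 list whose own definition carries an end point. The intrauterine, hormonal and vasectomised-partner entries have none, so criterion 11 governs them without conflict.

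The wording of Section 5.2.1 sharpens the problem. By setting abstinence beside the highly effective methods as an alternative, it allows the reading that the duration in criterion 11, which is attached to highly effective contraception, does not carry over to abstinence. A patient relying on abstinence can then meet the written definition by stopping when the study ends.

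What is at stake is a safety instruction in a first-in-human study. Sites should not have to infer when a preventive obligation ends. No endpoint or analysis is affected.

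**Working it through.** **1. The passages side by side**

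| Source | Applies to | Stated end point |
|---|---|---|
| 5.1, criterion 11 | Patients, or partners, of childbearing potential | Study, plus a redacted period after the last dose |
| 5.2.1 | Those using true abstinence | End of study |
| 5.2.1.2, abstinence entry | Those using true abstinence | End of study |
| 5.2.1.2, condom rule | Male participants | Study, and at least 5 months after the last dose |

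The second and third rows lack the limb that the first and fourth contain.

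**2. Earliest scheduled end after the last dose**

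The inputs are the Period 2 dosing days, the visit days in Table 3, and the Period 1 visit days in Table 1.

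- Period 2 Cohort 1: Day 197 (EOS) − Day 113 (third dose) = 84 days; 84 / 7 = 12.0 weeks. This reproduces the plan's stated minimum.
- Period 1: Day 85 − Day 1 = 84 days, the same minimum.
- Period 1 followed to Week 24: Day 169 − Day 1 = 168 days.
- Visit windows in Period 2 (Day 113 ±3, Day 197 ±5): shortest 192 − 116 = 76 days, longest 202 − 110 = 92 days.

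**3. The one post-dose window that can be read**

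5 months = 5 × 365.25 / 12 = 152.2 days, or 21.7 weeks. It is stated only for male condom use.

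**4. Shortfall measured against that window**

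Shortfall = max(0, W − F), where W is the required window and F the days from last dose to end of study.

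- F = 84: 152.2 − 84 = 68.2 days (9.7 weeks).
- F = 76: 76.2 days. F = 92: 60.2 days.
- F = 168: zero, because 168 exceeds 152.2.
- With 28-day months and F = 84: 140 − 84 = 56 days.

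**5. What this means for women**

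For women, W is the redacted period in criterion 11. If that period were 84 days or less, a patient at the scheduled minimum would have no shortfall. If it were 5 months, the shortfall would be about 68 days. The documents do not show which applies.

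**The case against.** The strongest reply is that criterion 11 already settles duration. Section 5.2.1 opens by referring back to the inclusion criteria, and criterion 11 points forward to Section 5.2.1.2 for the methods. On that reading the criterion says how long and the section says which methods count, so a patient who ends abstinence at the last visit still owes another method for the rest of the window. This is reasonable and many sites may read it so. It does not remove the conflict: the same section treats abstinence as an alternative to the methods that criterion 11 extends, and both definitions state a shorter limit without qualification.

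Other parts of the objection stand and limit the claim.

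- **Men.** The condom rule is additional and has no exemption for those relying on abstinence. A man who stops abstaining at the end of the study remains bound by it.
- **Women.** A reader might infer that a general 5-month window exists and that 68 of 152 days (45%) go unprotected. The documents do not support this, because the 5 months is written for male condom use and the general figure is redacted.
- **Timing.** A reader might infer that every patient's obligation ends at 84 days. That is the scheduled minimum. Period 1 follow-up can reach 168 days, patients who stop dosing early are encouraged to stay in the study, and Section 15.4 permits a reading under which the study ends with the last patient's last visit.
- **Residual drug.** Equating 5 months with 5 half-lives implies a half-life of about 30.4 days, giving 0.5^(84/30.4) = 15% remaining at 84 days against 0.5^5 = 3% at 5 months. A reader might take this as evidence of fetal risk. It assumes simple first-order decay and a half-life worked back from one parenthesis that names no matrix, and nothing visible links 15% to reproductive harm.

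**Conclusion.** The text is wrong as written, in a limited form. Two definitions of an accepted method end with the study, while the criterion they serve adds a period after the last dose. This is a contradiction in stated text and does not depend on what the redaction hides. It bears chiefly on female patients relying on abstinence.

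The size is conditional. The definition can be met by stopping as early as 84 days after the last dose. Against the male condom window of about 152 days the shortfall is about 68 days, or 60 to 76 with visit windows. This assumes that the study ends, for the patient, at her own final visit and that she is followed only for the scheduled minimum. Whether women face any shortfall, and how large, cannot be confirmed from the public text.

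**What to change.** Criterion 11 in Section 5.1 (and its copy in the synopsis), Section 5.2.1 and Section 5.2.1.2 must be reconciled so that the abstinence definitions and the contraception criterion state a consistent end point. The reconciled text should also say whether abstinence counts as one of the highly effective methods or as an alternative to them, and whether the end of the study means the patient's own final visit or the date in Section 15.4. No duration is proposed here.

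The cost is about one phrase in each of Sections 5.2.1 and 5.2.1.2, with a check that the consent wording matches; the consent pages were not available for this review. No visit, sample size or analysis changes.

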5.2.1.1 Non-Childbearing Potential

Non-childbearing potential is defined as a female who meets either of the following criteria:

- Postmenopausal state defined as no menses for 12 months without an alternative medical cause
- Documented hysterectomy, bilateral tubal ligation, or bilateral oophorectomy

5.2.1.2 Highly Effective Methods of Contraception

Contraception methods that can achieve a failure rate of <1% per year when used consistently and correctly are considered highly effective birth control methods. Such methods are defined as one of the following:

- True abstinence, defined as refraining from heterosexual intercourse for the duration of the study, when in line with the preferred and usual lifestyle of the patient
- Vasectomized partner (if that vasectomized partner is the sole sexual partner and has received medical assessment of the surgical success of the vasectomy)
- An intrauterine hormone-releasing system (IUS).
- Combined (estrogen and progesterone containing) hormonal contraception associated with inhibition of ovulation (oral, intravaginal or transdermal combined)
- Progesterone-only hormonal contraception associated with inhibition of ovulation (oral, injectable, or implantable)
- An intrauterine device (IUD)

In addition, male participants must be required to use a condom, as contraception requirement, for the duration of the study and, at minimum, until 5 months (i.e., 5 elimination half-lives) after the last WVE-003 dose.

Note that periodic abstinence (calendar, symptothermal, post-ovulation methods), withdrawal (coitus interruptus), spermicides only, and lactational amenorrhoea are not acceptable methods of contraception.

5.3 Withdrawal and Discontinuation

Patients are free to withdraw from the study or discontinue treatment with study drug at any time upon request without prejudice to their future medical care by the Investigator or at the study site. Patient participation in the study may also be stopped at any time at the discretion of the Investigator or at the request of the Sponsor, as described in [Section 5.3.1](#). Patients who withdraw or discontinue from study treatment will no longer receive study drug.

5.3.1 Withdrawal of Patients From the Study

Patients must be withdrawn from the study for any of the following:

- Patient's withdrawal of consent
- At the discretion of the Investigator for medical reasons
- At the discretion of the Investigator or Sponsor for noncompliance
- Significant protocol deviation
- Termination of the study by the Sponsor (see [Section 14.4](#) for additional details)

In addition, the Sponsor may withdraw a patient from the study at their discretion and for any reason.

Any patient for whom consent to participate in the study is withdrawn will be removed from further treatment and study observation immediately upon the date of request. It should be encouraged that these patients complete the early termination study procedures ([Section 4.1.5](#)) and observations at the time of withdrawal. All information, including the reason for withdrawal from the study, must be recorded in the eCRF and source documentation.

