Abbreviations: CBC = complete blood count; CRP = C-reactive protein; CSF = cerebrospinal fluid; D = day; ECG = electrocardiogram; ET = early termination; h = hour; m = minute; PBMC = peripheral blood mononuclear cell; PD = pharmacodynamic(s); PK = pharmacokinetic; W = week.

^a Predose on all dosing days, CSF sample will be collected approximately 15 minutes prior to study drug administration. At all noted time points, approximately 20 mL of CSF total should be collected. CSF samples must be tested locally for safety for the following parameters: total protein, glucose, and cell counts (white blood cell counts with differential) on all noted visits.

^b This lumbar puncture is optional for patients who terminate early.

- Electrocardiogram recordings will be obtained in the supine position after the patient has rested comfortably for ≥ 10 minutes. At time points when plasma PK is also being collected, the ECG should be performed first, and PK should be collected within 30 minutes after (and within the applicable postdose window).
- Parameters to be assessed are detailed in [Table 6](#). Clinical laboratory safety assessments will be performed up to 1 week prior to dosing on all dosing days. Note that these assessments also include CBC, CRP, complement, and fibrinogen.
- Assessments from the last in-clinic visit in Period 1 may be used if the last in-clinic visit occurred within 4 weeks prior to the Confirm Eligibility visit for Period 2.

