5.3.2 Discontinuation of Study Drug

A patient must permanently discontinue treatment with study drug for any of the following reasons:

- The patient is withdrawn from the study ([Section 5.3.1](#)).

- The patient experiences a serious or intolerable AE (as defined in [Section 9](#)) that, in the Investigator's opinion, requires treatment discontinuation.
- A change in the patient's medical condition not consistent with the protocol requirements or that justifies withdrawal from the study or study drug
- Pregnancy (refer to [Section 10](#))
- Patients with renal, hepatic, platelets, clotting time, and inflammatory laboratory values that are severe (i.e., CTCAE Grade 3) or higher and/or considered clinically significant, in the opinion of the Investigator, will temporarily discontinue treatment and be retested every 2 weeks until resolution of laboratory abnormalities. Patients with renal or hepatic laboratory values that are serious (i.e., CTCAE Grade 4) will be permanently discontinued from treatment and will be retested every 2 weeks until resolution.

If a patient discontinues treatment, they will be encouraged to remain in the study to be monitored and to complete all study-related procedures, unless consent is withdrawn. Patients who discontinue treatment due to an AE ([Section 9](#)) or pregnancy ([Section 10](#)) may require longer follow-up.

The reason for discontinuation of treatment with study drug must be recorded in the eCRF and source documentation.

5.3.3 *Lost to Follow-up*

Patients who fail to return for final assessments will be contacted by the site in an attempt to have them comply with the protocol. A minimum of 3 documented contact efforts should be made on different days over the course of 2 weeks. If the patient is unreachable by telephone, a registered letter will be sent to the patient requesting him or her to contact the study center. If contact with the patient is not established after all above attempts, this patient will be considered as lost to follow-up.

5.3.4 *Replacements*

Patients will be replaced in accordance with the requirements for dose escalation.

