Period 1 Urine PK: Samples will be collected on Week 0/Day 1 from 0-4 hours, 4-8 hours, and 8-24 hours postdose.

Period 1 CSF PK: Samples will be collected predose on Week 0/Day 1, as well as Week 2, Week 4, Week 8, and Week 12. A sample will also be collected at the ET visit, if the patient discontinues early.

Period 2 Plasma PK: At the first and last dosing visit, blood samples will be collected predose (within 4 hours prior to dosing), and postdose at 30 minutes (± 5 minutes), 1 hour (± 15 minutes), 2 hours (± 15 minutes), 4 hours (± 30 minutes), and 6 hours (± 30 minutes). New patients only will also have a sample collected on Day 1 at 24 hours (± 2 hours) postdose. For any other dosing visit, blood samples will be collected at 2 hours (± 1 hour) postdose. In addition, plasma PK samples will be collected once at all non-dosing clinic visits. A sample will also be collected at the ET visit, if the patient discontinues early.

Period 2 CSF PK: Samples will be collected at all clinic visits (Week 0/Day 1, Week 4, Week 8, Week 12, Week 16, Week 20, Week 24, and Week 28). The sample will be collected predose on dosing visits. A sample will also be collected at the ET visit, if the patient discontinues early.

The date and time of the sample collection will be recorded.

Samples will be analyzed by a central laboratory to determine concentrations of WVE-003 using validated methods (plasma and CSF) or qualified methods (urine).

Samples will only be used by the Sponsor and/or a contracted vendor for research related to the development of treatments for HD and stored for a maximum of 10 years. All biological material will be stored and secured in a way that ensures that unauthorized access is prohibited and the samples are not lost, deteriorated, or destroyed accidentally or illegally. Detailed instructions for sample collection, storage, processing, and shipping will be provided in the Laboratory Manual.

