15.3 Management of Protocol Amendments and Deviations

15.3.1 *Modification of the Protocol*

Any changes in this research activity, except those necessary to remove an apparent, immediate hazard to the patient, must be reviewed and approved by the Sponsor or designee. Amendments to the protocol, other than minor clarifications and typographical corrections, must be submitted in writing to the Investigator's IRB/EC and regulatory authorities for approval before patients can be enrolled into an amended protocol.

15.3.2 *Protocol Deviations*

A deviation from the protocol is an unintended or unanticipated departure from the procedures or processes approved by the Sponsor and the IRB/EC. A major protocol deviation is any deviation that impact the completeness, accuracy, and/or reliability of the study data or that may significantly affect a patient's rights, safety, or well-being.

The Investigator or designee must document and explain in the patient's source documentation any deviation from the approved protocol. The Investigator may implement a deviation from the protocol to eliminate an immediate hazard to study patients without prior IRB/EC approval. As soon as possible after such an occurrence, the implemented deviation, the reasons for it, and any proposed protocol amendments should be submitted to the IRB/EC for review and approval, to the Sponsor for agreement, and to the regulatory authorities, if required. Any deviation from the study protocol that is due to COVID-19 considerations should be noted as such.

Protocol deviations will be documented by the clinical monitor in the clinical study management system and on monitoring reports throughout the course of monitoring visits. Investigators will be notified in writing by the monitor of deviations. As required by local regulatory authorities, the Investigator will notify the IRB/EC of any applicable protocol deviations in a timely manner.

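### A significant protocol deviation, a term the protocol leaves undefined, forces withdrawal from the study and so ends scheduled follow-up of patients already dosed

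*Combined protocol and SAP*

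**What the plan says.** Section 5.3.1 opens its list with "Patients must be withdrawn from the study for any of the following". Among the entries is "Significant protocol deviation", which stands alone. The entry for noncompliance is different, because it is left to the judgement of the investigator or sponsor.

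The protocol does not define *significant*. Section 15.3.2 defines a different term: "A major protocol deviation is any deviation that impact the completeness, accuracy, and/or reliability of the study data", or one that may significantly affect the patient's rights, safety or well-being. That section attaches no withdrawal to a major deviation.

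For a patient who stops drug but is not withdrawn, Section 5.3.2 says "they will be encouraged to remain in the study to be monitored and to complete all study-related procedures", unless consent is withdrawn. The same section makes withdrawal from the study a reason for permanent discontinuation of study drug.

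For a patient who leaves the study, Section 4.1.5 says: "If a patient withdraws from the study early, the patient should complete an early termination visit". On the CSF sample at that visit, a footnote to Table 4 says: "This lumbar puncture is optional for patients who terminate early".

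**The concern.** The primary objective is safety and tolerability. A deviation can be recorded and dealt with in the analysis, and nothing about it requires observation to stop. Under the rule as written, a patient who has received an intrathecal oligonucleotide leaves scheduled monitoring because of an event after randomization.

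Two things are at stake. The first is safety capture in an exposed patient. The second is the PD and clinical-effects analysis, a mixed model for repeated measures in which later visits go missing by rule. If deviations are related to tolerability or outcome, the missing-at-random assumption behind that model may fail. The undefined trigger adds to this, since sites could apply it differently.

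**Working it through.** The documents give no power, effect size, SD, dropout rate or deviation rate, so there is no stated figure to reproduce. The check compares the sections and adds two small calculations.

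**What remains after withdrawal under Section 5.3.1**
- One early termination visit is expected (4.1.5). It includes a plasma PK sample (8.3) and an optional lumbar puncture (Table 4).
- SAEs are followed to resolution (9.3.3).
- Adverse events count as on-treatment only until the patient completes or leaves the study (11.3.4).
- SAEs are reported regardless of cause only up to the early termination or end-of-study visit. Related SAEs that start later go to the sponsor but are not entered in the eCRF (9.3.4.1).
- Nothing extends the encouragement in 5.3.2 to a patient whom 5.3.1 has removed. Section 4.1.4.4, which requires all Period 2 patients to complete follow-up for at least 12 weeks after the last dose, makes no exception for deviations and does not override 5.3.1.
- Section 5.2.1.2 equates 5 months with 5 elimination half-lives, about one month per half-life, so exposure could outlast observation.

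**Period 2 CSF visits lost**

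Section 8.3 schedules CSF at Day 1 and at Weeks 4, 8, 12, 16, 20, 24 and 28, which is 7 post-baseline visits.

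| Withdrawn just after | Scheduled CSF visits lost |
|---|---|
| Week 4 | 6 of 7 |
| Week 8 | 5 of 7 |
| Week 12 | 4 of 7 |
| Week 16 | 3 of 7 |

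At most one optional sample replaces them. In P2C1 the last dose is at Week 16, so withdrawal just after it removes the scheduled visits of the whole 28 − 16 = 12 weeks of post-dose follow-up.

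**Precision (illustration)**

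P2C1 plans about 24 patients (4.1.4.2). The Period 2 allocation ratio is not stated, so the splits below are assumptions. In SD units, SE = √(1/a + 1/p), with a active and p placebo patients.
- 2:1 (16 and 8): √(1/16 + 1/8) = 0.433.
- One placebo patient lost: √(1/16 + 1/7) = 0.453, a rise of 4.7%.
- Two placebo patients lost: √(1/16 + 1/6) = 0.479, a rise of 10.6%.
- 1:1 (12 and 12), one placebo patient lost: √(1/12 + 1/11) / √(1/12 + 1/12) = 0.417 / 0.408, a rise of 2.2%.
- 3:1 (18 and 6), one placebo patient lost: √(1/18 + 1/5) / √(1/18 + 1/6) = 0.506 / 0.471, a rise of 7.2%.
- 2:1, one active patient lost: √(1/15 + 1/8) = 0.438, a rise of 1.1%.

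These are upper bounds, because they treat a withdrawn patient as contributing nothing, whereas the mixed model uses visits before withdrawal.

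**Analysis provisions**

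Section 11 describes no sensitivity analysis for missing visits. The one it names concerns the choice of baseline for rollover patients (11.3).

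**The case against.** The strongest defence is that 5.3.1 and 5.3.2 govern different events, leaving the study and stopping drug, so they do not contradict each other. It adds that the protocol softens the loss and that blinding of patients, site staff and the sponsor's conduct staff (7.1) limits treatment-dependent selection. The affected PD and clinical analyses are exploratory, and the sample size was not based on hypothesis testing. All of this is fair and limits the weight of the point. It does not supply the missing follow-up.

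Four stronger readings are tempting, and the documents do not support them.
- *Noncompliance also forces withdrawal.* It does not; that entry is discretionary.
- *The patient's data are discarded and the patient is lost to all safety observation.* Data already collected are kept, and dosed patients stay in the safety population (11.2.1). An early termination visit is expected and SAEs are followed to resolution. Immediate removal from observation is written only for withdrawal of consent. What stops is further scheduled collection.
- *Tolerability-driven events, such as a missed lumbar puncture, are shown to trigger the rule.* No examples are given. Section 4.4.5 records assessment changes caused by COVID-19 as deviations without requiring withdrawal, and Section 8.2.2 allows any concomitant medication judged necessary.
- *The 5% and 11% are expected losses.* They rest on an assumed ratio and on zero contribution from withdrawn patients. Placebo patients are also pooled (Section 11), so the control group could be larger if further cohorts open.

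One objection bears on the remedy. Because 5.3.2 ties permanent drug discontinuation to study withdrawal, simply deleting the entry would also remove a drug stop without saying so.

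**Conclusion.** The point holds in a limited form. Study withdrawal for a significant deviation is mandatory, the trigger is undefined, and no other section keeps such a patient in scheduled follow-up. The consequence that follows directly from the documents is the loss of 3 to 6 of 7 post-baseline CSF visits for withdrawal just after Weeks 4 to 16 of Period 2, together with the scheduled safety monitoring at those visits.

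Informative missingness is possible if deviations relate to tolerability, but neither its size nor its direction can be derived. The loss of precision is at most about 5% for one placebo patient and 11% for two under the assumed 2:1 split. For one placebo patient it ranges from about 2% at 1:1 to 7% at 3:1. The gap in safety capture does not depend on the ratio. The change should be made: the rule yields poorer safety and PD data and is easy to correct.

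**What to change.** 1. In Section 5.3.1, take significant protocol deviation out of the mandatory study-withdrawal list.
2. State that such patients continue all scheduled safety, PK, PD and clinical assessments unless consent is withdrawn.
3. If the term *significant* is kept anywhere, define it and state how it relates to *major* in Section 15.3.2.
4. Reconcile 5.3.1 with 5.3.2 so that the existing consequence of a significant deviation for study drug is stated explicitly and is not changed by this edit. What that consequence should be is for the sponsor, not this review.
5. Record the deviation and add a sensitivity analysis in Section 11 or the SAP that examines these patients and any missing visits.
6. Leave noncompliance withdrawal discretionary. At most, add that these patients are encouraged to remain in follow-up.

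The cost is a few sentences and continued visits for a few patients. Those visits are already in the schedule of assessments.
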